To ensure proper autonomic and hemodynamic response to exercise, BP will be taken before, during (minute 20), and following cool-down. During exercise sessions, pedaling torque, cadence and HR will be continuously recorded at 60Hz and rate of perceived exertion (RPE) will be recorded every 10 minutes using our previous methods.⁵ The main exercise set (40 min) and HR (60-80% of HHR)⁶ will be identical across FE and VE. The single manipulated independent variable is pedaling cadence. For the VE group, maximum cadence will be limited to 60rpms. During FE, with assistance of the motor, cadence will be maintained between 80-90rpms.⁶ This approach replicates previous human and animal exercise paradigms and will lead to clear interpretation of the effect of cadence on STN neural activity and upper extremity motor function.

Forced-exercise (FE) Cycle and Session: To deliver the FE intervention, a suite of sensors is integrated into a standard stationary cycle to monitor system and rider status. The inertia wheel, brake and brake controller

[figure not shown]

Figure 1: Illustration of experimental protocol and equipment utilized to obtain LFPs from STN-DBS implanted in PD patients during exercise. (A) Percept PC system is integrated into the implantable pulse generator (IPG) shown in circle insert and continuously transmits LFPs in real time wirelessly to a storage device (tablet) (B) Illustration of the DBS lead implanted in the subthalamic nucleus (STN) and surrounding basal ganglia nuclei (C) Assessments, MDS-UPDRS-III and force-tracking, will be performed at 3 time points during an experimental session.

were replaced with three core components: servomotor, motor-drive, and programmable controller. While the motor augments pedaling rate in the FE mode, participants actively contribute to pedaling as they must exercise within their specified target HR range. The control algorithm automatically adjusts assistance or resistance during FE based on the user's continuously-monitored torque production and heart rate thus allowing the system to maintain an effective therapeutic cadence while the user maintains their target heart rate.

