Voluntary Exercise (VE) Session: During the VE session, individuals will complete the main exercise set at a cadence of no greater than 60rpms⁶ on the same stationary cycle while in its standard voluntary mode. In the event that a participant's voluntary rate is >60rpms, resistance will be applied to ensure cadence is maintained and target HR is reached. In standard voluntary mode the motor control assistance algorithm is disabled and the cycle functions as a typical resistance based stationary cycle. During the VE exercise session, pedaling torque, cadence and HR will be continuously recorded at 60Hz and RPE will be recorded as in the FE session.

DATA COLLECTION

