Local Field Potentials (LFP) Recordings: Neural activity of the STN will be gathered bilaterally for the duration of each 130-minute visit. Medtronic's BrainSense Indefinite Streaming platform will provide LFP data from Medtronic 3389 electrode model or SenSight directional leads. For the **On-DBS epoch**, LFPs from contact pairs surrounding the stimulating contact (0-2, 0-3, 1-3) for each hemisphere will be recorded (2 channels total).⁷ In the **Off DBS, Exercise and Post-exercise epochs**, LFPs will be recorded between contact pairs 0-2, 0-3, 1-3 bilaterally resulting in simultaneous recordings of 3 channels per hemisphere (6 channels total). All LFP recording will be sampled at 250Hz and low-pass filtered (0-100Hz) and streamed via Bluetooth to the Medtronic tablet (Figure 1A&B). While in the Off DBS epoch, the bipolar channel with highest peak power in the beta band (13–35 Hz) during rest in each hemisphere will be selected for further analyses. This selection is based on previous studies demonstrating a significant correlation between contact-pair location in the sensorimotor portion of the STN and beta power.⁸ **LFP outcomes:** Prior to calculation of outcomes, windows containing movement artifacts will be visually identified by large fluctuations in the time series and high amplitude broadband activity in the spectrogram and removed from further analysis. Triggered spectrograms will be calculated for each trial using the multitaper method with a 500 ms, 250 ms overlap moving window, 2.0 Hz frequency resolution, and 1 taper. Relative power will be obtained for each subject and frequency by normalizing the absolute power by its average across time for each channel. This approach will facilitate comparison across subjects, whose absolute signal magnitude can vary by one or two orders of magnitude. The relationship of synchronization and desynchronization changes in oscillatory activity within the frequency bands of interest, delta, theta, alpha, beta and gamma bands, will be calculated across each of the four epochs within an experimental session. Along with average power, moment-to-moment dynamics of the band power, e.g., beta bursts, will be assessed in each condition as previous data indicate beta burst activity during continuous movement is related to PD bradykinesia.⁹ [name] will lead the collection and analysis of LFP data.

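### If pedaling leaves artifact in the LFP, exercise-epoch changes in delta, theta and alpha, and any FE-versus-VE reading of them, could be partly mechanical, and the visual artifact rule is not suited to it

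*Combined protocol and SAP*

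**What the plan says.** The APPROACH section makes cadence the contrast between the two visits: "The single manipulated independent variable is pedaling cadence". The two settings are "For the VE group, maximum cadence will be limited to 60rpms" and "During FE, with assistance of the motor, cadence will be maintained between 80-90rpms". The main set lasts 40 minutes in both modes. The section expects that this design "will lead to clear interpretation of the effect of cadence on STN neural activity and upper extremity motor function".

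Under DATA COLLECTION, Local Field Potentials (LFP) Recordings, LFPs are recorded throughout each 130-minute visit, including while the participant pedals. Changes in delta, theta, alpha, beta and gamma activity "will be calculated across each of the four epochs within an experimental session". The spectral settings are a 500 ms window, 2.0 Hz resolution and one taper. Power is normalized by its time average for each channel, and the time span of that average is not given. Only beta has stated limits (13-35 Hz).

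The one artifact control is that "windows containing movement artifacts will be visually identified by large fluctuations in the time series and high amplitude broadband activity" in the spectrogram, after which those windows are dropped. Torque and cadence are recorded at 60 Hz, but no use of them to check or clean the LFP is described.

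The Aim 1 Statistical Analysis uses 90 seconds at rest before and after exercise, both for the primary test (reduction after exercise) and for the secondary test (FE against VE).

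**The concern.** The variable that defines the two modes also sets the frequency of any movement artifact. Randomizing the order of FE and VE cannot balance this, because the frequency belongs to the mode and not to the visit.

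The visual rule is designed for conspicuous broadband events. A small, steady, narrow-band rhythm need not look like one and could pass. A larger rhythm could cause many exercise windows to be dropped, and more in one mode than in the other. Either way, a low-band change from rest to exercise could be partly mechanical. If the FE and VE visits are then set side by side, so could the difference between modes.

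At stake is the interpretation of the exercise epoch in the low bands, where the plan expects a clear reading of the effect of cadence on STN activity.

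**Working it through.** The plan gives no figure to reproduce. The check has four steps.

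**1. Pedaling frequencies.** Hz = rpm / 60, doubled for two leg pushes per turn.
- VE: 60/60 = 1.00 Hz per turn and 2.00 Hz per push, both upper limits because no minimum cadence is given.
- FE: 80/60 = 1.33 to 90/60 = 1.50 Hz per turn, and 2.67 to 3.00 Hz per push.
- Harmonics 3 to 8 of the turn rate: 3-8 Hz for VE at 60 rpm, 4-10.7 Hz for FE at 80 rpm, 4.5-12 Hz for FE at 90 rpm.

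With assumed limits of delta 1-4, theta 4-8 and alpha 8-13 Hz, the turn and push rates lie in or at the edge of delta. Harmonics reach theta in both modes and extend into alpha in FE.

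**2. Resolution.** A 500 ms window holds 0.5 x 1.00 = 0.50 turn in VE and 0.5 x 1.33 = 0.67 to 0.5 x 1.50 = 0.75 turn in FE. Bin spacing is 1/0.5 s = 2 Hz. The two turn rates cannot be separated from each other or from delta activity.

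**3. Artifact alone.** Sinusoids of equal amplitude were passed through a 500 ms single taper.
- Once per turn, 1-4 Hz: FE/VE power is 1.26-1.28 at 80 rpm and 1.39-1.42 at 90 rpm, depending on implementation. On the native 2 Hz bins it is 1.40-1.57.
- Twice per turn, 4-8 Hz: about 0.85% of artifact power leaks into the band in VE, against 6.0% (80 rpm) and 12.5% (90 rpm) in FE. The ratios are 6.0/0.85 = 7.1 and 12.5/0.85 = 14.7, but all three are small leakages. With a 4 s window the shares are about 0.0003% and 0.0006-0.0008%.

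**4. Artifact added to a background.** The same 1/f background was used in both modes, so the true FE/VE ratio is 1.

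| Assumed artifact | Delta | Theta | Alpha | Beta |
|---|---|---|---|---|
| Sinusoid, 0.25-1 background SD, no normalization | 1.02-1.32 | up to 1.95 | not tabulated | unchanged |
| Same, normalized over the whole session | at most 1.18 | at most 1.25 | not tabulated | unchanged |
| Separate run, sine once per turn, amplitude 0.5-2 SD | 1.10-1.69 | 0.96-1.00 | 0.98-1.00 | 0.98-1.00 |
| Separate run, sine twice per turn, amplitude 0.5-2 SD | 1.02-1.11 | 1.00-1.10 | 1.00-1.05 | 1.00-1.03 |
| Separate run, sharp pulse per push, same power as the sines | 0.89-1.00 | 1.17-3.07 | 1.01-1.62 | 1.00-1.03 |

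The runs differ on theta for a twice-per-turn sine (up to 1.95 against up to 1.10). The size therefore depends on implementation as well as on the artifact.

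**Normalization and the resting windows.** If the time average spans the whole 130-minute session, and exercise-epoch power is m times resting power for 40 minutes, the denominator is multiplied by (90 + 40m)/130. This gives 170/130 = 1.31 for m = 2, 210/130 = 1.62 for m = 3 and 290/130 = 2.23 for m = 5. A post/pre ratio within a session cancels this factor; a post-minus-pre difference does not.

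**The case against.** **No formal test is touched.** The sentence on the four epochs describes changes within one session, and FE and VE take place on separate days. The only specified FE-versus-VE test of band power uses resting windows. This stands. A reader might infer that the Aim 1 mode comparison is contaminated, and the documents do not support that. Two qualifications remain. Rest-to-exercise change within a session can carry artifact without any mode comparison. And the stated aim of interpreting the effect of cadence invites the two visits to be compared.

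**The sizes can be made to look dramatic.** A reader might infer a 7- to 14-fold false difference in theta. That figure is a ratio of small leakages with no brain signal in the denominator. With a twice-per-turn sine at 0.25-0.5 background SD, the theta ratio is only 1.02-1.21. Larger values need artifact near or above the background SD, or a sharp waveform. Whole-session normalization shrinks the effect further. If power were normalized within the epoch, average exercise power would be 1 in both modes, and any real mode difference would vanish too.

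**Artifact may be absent or small.** Recording is bipolar, the cycle is recumbent with an upright back, and the visual rule removes the largest disturbances, perhaps only some windows. This is fair: it cannot be said that delta and theta would differ through mechanics alone. But nothing in the plan would show whether artifact is present.

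**Cleaning is not free.** No common time base is described for the cycle signals and the LFP stream, which goes by Bluetooth to a tablet. Cleaning would also remove STN activity genuinely locked to the pedal cycle. Both points stand and shape the fix.

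**Conclusion.** The concern holds as a conditional one. Cadence differs by design, band outcomes are planned for the exercise epoch, and the stated rule does not suit a continuous narrow-band rhythm. If pedaling artifact is present, exercise-epoch findings in delta, theta and possibly alpha could be partly mechanical.

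Under the sinusoidal assumption at 0.25-1 background SD, the false FE/VE ratio is about 1.0-1.3 in delta and 1.0-1.95 in theta before normalization. Sharper artifact could reach alpha. Beta stays within about 3% of 1 in every case run; gamma was not calculated. These figures rest on assumed band limits, equal artifact size in both modes, VE at exactly 60 rpm and a 1/f background. They show what is possible, not what will occur.

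The primary and secondary Aim 1 tests are not directly affected. An indirect route exists only if the normalization average includes the exercise epoch and change is taken as a difference. The point merits a change to the LFP analysis text; it does not undermine the trial's main tests.

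**What to change.** Add to the LFP outcomes text, for the exercise epoch:
- Check coherence between the LFP and the recorded cadence and torque signals.
- Report delta, theta and alpha power both with and without removal of the component at the pedaling frequency and its harmonics. Align the cycle and LFP time bases first; if that is not possible, use a notch that tracks cadence.
- Report the number of windows removed, by mode.
- If artifact cannot be excluded, draw no neural conclusion from exercise-epoch FE-versus-VE differences in delta, theta or alpha, and rest mode conclusions in those bands on the resting windows.

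It would also help to state the limits of every band and the time span of the normalization average.

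The cost is analysis code, a few sentences and a check on time alignment. The reference signals are already planned, and enrollment, visits and the resting tests are unchanged. The downside is that the cleaned estimate also loses genuine pedal-locked STN activity, which is why both versions should be reported.

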The Impact of Exercise on Subthalamic Nucleus Neural Activity in Parkinson's Disease

Study Protocol

NCT05905302

Document Date 2/14/2023

Posted 9/16/2025

Project Title: The impact of exercise on subthalamic nucleus neural activity in Parkinson's disease

PI: [name]

Version Date: 2/14/2023

APPROACH

Fifteen PwPD utilizing the Percept PC DBS system will be enrolled for this project. Briefly, all patients will be at least six-months post bilateral DBS surgery with DBS parameters clinically optimized for at least three months prior to enrollment. To reduce possibility of a cardiac adverse event during the proposed exercise sessions, the American College of Sports Medicine (ACSM) Pre-exercise Screen¹ will be performed prior to exercise (see Protection of Human Subjects for details). We anticipate an ample population of PwPD eligible for recruitment as neurosurgeons within the Center for Neurological Restoration (CNR) perform 200 bilateral STN DBS surgeries annually. The Percept platform is rapidly becoming the system of choice due to ease of programming.

Following all pre-screening, participants will complete three visits on 3 separate days. For **Visit 1**, participants will complete the informed consent process, establish resting heart rate (HR; supine x 5 min), be fitted to the cycle to ensure proper mechanics, complete ~5-10 minutes of FE and VE to ensure safety and understand cycle operation, complete 5-10 familiarization force-tracking trials,² and have order of FE or VE assigned for Visit 2 and 3 via a computerized randomization scheme. Target HR will be calculated using the Karvonen method³ [(Max HR-Resting HR) x (60%-80%) + Resting HR]; max HR will be estimated as (220-age).⁴ Figure 1 provides an overview of the experimental paradigm for Visit 2 and 3.

For **Visit 2 and 3**, PwPD will arrive OFF antiparkinsonian medication and On-DBS. The 130-minute experimental session will be divided into four epochs: 1) On-DBS, 2) Off-DBS, 3) Off-DBS + Exercise and 4) Post-exercise. Neural activity from the STN will be continuously recorded from both DBS electrodes for the entire 130-minute session.

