Force-tracking: Upper extremity motor control will be assessed during the performance of a force-tracking task used previously with older adults^{10,11} and PwPD.^{2,12} Patients will use a precision grip (thumb and index finger) with the dominant hand to exert an isometric force against a six-degree of freedom force transducer (Figure 1C) affixed to an adjustable experimental table. The greatest force produced in the F_Z axis (grip force) during a five second trial will be considered their maximum voluntary contraction (MVC). To ensure consistent motor task demands across the four data collection timepoints, target tracking force will be 20% of their MVC for a given session. During the force-tracking task, participants match their grip force to the target force as accurately as possible; a monitor simultaneously displays target force and patient produced grip force.

Force-tracking Outcomes: Force data will be filtered with a phase-symmetric low-pass filter employing Woltring's algorithm using existing Matlab analysis programs.^{13,14} The primary outcomes will be time within the target range (TWR) and relative root mean square error (RRMSE). The TWR is calculated by determining the time the patient's force trace is within $\pm 2.5\%$ of the target line. The TWR provides an overall accuracy measure of force-tracking. To account for differences in the amplitude of the target force (e.g. inter-patient and intra-patient variability due to stimulation or exercise status), the RRMSE will be used as a method of normalizing

performance relative to force amplitude. Where, $F_T(t)$ is the target force provided to the patient, $F_0(t)$ is the force produced by the patient, T trial time.

Aim 1: To determine the effects of two modes of high intensity exercise, FE and VE, on the pattern of neural activity within the STN.

Statistical Analysis: Average band powers (delta, theta, alpha, beta and gamma) will be calculated at rest for 90 seconds in the Off DBS session immediately prior to exercise and immediately following FE and VE sessions. Mixed effect models will be utilized for each band power to determine if band powers at rest while Off DBS are significantly reduced following high intensity exercise (primary outcome), and to determine if the FE reduces band power significantly more than VE (secondary outcome).

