Aim 2: To determine the relationship between changes in STN neural activity associated with FE and VE on upper extremity motor function and clinical symptoms of PD.

Statistical Analysis: The force-tracking outcomes, including TWR, will be calculated for all trials. Data from the Off DBS and Off DBS + Post Exercise sessions will be used for the primary analysis. Mixed effects models will be utilized to determine if force tracking performance improves following either exercise mode compared to Off-DBS and secondary analysis will be conducted to determine if FE improves force tracking more than VE. Clinical data from the same time points will be evaluated to determine the overall clinical response to high intensity exercise and any differential effects of exercise mode (FE vs. VE). Mixed models will be adjusted for confounding characteristics determined a priori, including sex, education, and PD severity. Model assumptions and model fit will be assessed, and variables will be transformed, as needed.

Inclusion Criteria:

- a) Adult with a diagnosis of PD by a movement disorders neurologist
- b) Previous placement, at least six months, of bilateral Medtronic Precept DBS as standard of care treatment for their PD.
- c) Stable and clinically optimized DBS parameters for three months prior to enrollment.
- d) Demonstrate the ability to safely mount and dismount a recumbent exercise cycle with an upright back.
- e) Willingness to withhold antiparkinsonian medication and DBS stimulation.
- f) Exercise clearance using the American College of Sports Medicine (ACSM) Pre-participation Health Screen
 - a. If the ACSM screen recommends medical clearance, the subject must obtain medical clearance by their health care provider prior to participation.
 - b. Those who choose not to obtain physician clearance will not be eligible for participation.

Exclusion Criteria:

- a) Diagnosis of dementia or any neurocognitive impairment that compromises the ability to provide informed consent.
- b) A musculoskeletal issue that limits one's ability to cycle
- c) Neurological disease other than Parkinson's disease (i.e. multiple sclerosis, stroke) that impacts motor or cognitive function
- d) Uncontrolled cardiovascular risk factor such as a current cardiac arrhythmia, uncontrolled hypertension, untreated deep vein thrombosis, etc.

REFERENCES

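### The primary pre-to-post test cannot separate exercise from time since DBS-off, so its result is a change over the session and not an exercise effect

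*Combined protocol and SAP*

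**What the plan says.** The sample size is given in APPROACH: "Fifteen PwPD utilizing the Percept PC DBS system will be enrolled for this project". Patients arrive off medication for Visits 2 and 3, and each session is "divided into four epochs: 1) On-DBS, 2) Off-DBS, 3) Off-DBS + Exercise and 4) Post-exercise". Randomisation covers only the order of the two exercise modes: at Visit 1 patients "have order of FE or VE assigned for Visit 2 and 3 via a computerized randomization scheme". No visit omits exercise.

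APPROACH also fixes the length of the exercise: "The main exercise set (40 min) and HR" are the same for forced exercise (FE) and voluntary exercise (VE).

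On recording, APPROACH states "Neural activity from the STN will be continuously recorded from both DBS electrodes for the entire 130-minute session". From DBS-off onwards the contact pairs stay the same, "resulting in simultaneous recordings of 3 channels per hemisphere (6 channels total" (DATA COLLECTION, Local Field Potentials).

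The Aim 1 analysis takes one 90-second rest window directly before exercise and one directly after it. It uses mixed models to "determine if band powers at rest while Off DBS are significantly reduced following high intensity exercise (primary outcome"; FE against VE is secondary. Aim 2 uses the same two time points to "determine if force tracking performance improves following either exercise mode compared to Off-DBS", and evaluates clinical data there as well. The named covariates, listed under Aim 2, are sex, education and PD severity.

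**The concern.** Aim 1 asks what exercise does to STN activity. The test that carries that question compares an earlier with a later point of the same session, and exercise is not the only thing that happens between them. Time since DBS-off and time since medication withdrawal both increase as well, by the same minimum amount in every patient at every visit. If resting band power moves with either, the movement is counted as an exercise effect.

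The plan has nothing that could pull the two apart. The named covariates do not change within a session. Dividing power by a channel's time average rescales the series but leaves any trend in it. No term for minutes since DBS-off, no earlier Off-DBS window and no drift sensitivity analysis is specified.

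A significant primary result could therefore be read as an effect of exercise when it reflects time off treatment. A null result could equally hide a real effect. In Aim 2, repetition of the force task and fatigue are further explanations for a within-session change.

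**Working it through.** **Inputs from the documents.** n = 15; fixed epoch order; exercise at both visits; main set 40 minutes, so the windows are at least 40 minutes apart (warm-up and cool-down lengths are not in the text). The plan states no alpha, SD, effect size or power, so there is no figure of its own to reproduce.

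**Assumptions.** Two-sided 5% paired test; drift expressed in SDs of the within-patient change.

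**1. Identifiability.** Let f(t) be resting power at time t after DBS-off without exercise, e the exercise effect, and L ≥ 40 minutes the gap between windows. Then

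post − pre = e + [f(t+L) − f(t)] = e + δ.

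Every session contributes e + δ and none contributes δ alone, so the two cannot be separated. For the mode contrast, (e_FE + δ) − (e_VE + δ) = e_FE − e_VE: drift common to both visits cancels. A simulation with an equal drift of 0.5 SD in both sessions gave a two-sided rejection rate of 0.049.

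**2. Sensitivity to downward drift, with e = 0.** The test statistic is noncentral t with 14 df and noncentrality d√15. The critical value is 2.145.

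| Drift d (SD) | d√15 | Chance of declaring a reduction |
|---|---|---|
| 0 | 0 | 2.5% |
| 0.2 | 0.775 | 10.8% |
| 0.3 | 1.162 | 19.0% |
| 0.5 | 1.936 | 43.8% |

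A simulation at d = 0.5 gave 43.9%. Averaging the two visits divides the SD by 1/√((1+ρ)/2), where ρ is the correlation between the two visits' changes. At d = 0.5 the chance becomes 54.8% (ρ = 0.5) or 72.2% (ρ = 0). A larger sample makes it worse: at d = 0.3, 19% with 15 patients becomes 36% with 30.

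**3. Sensitivity to upward drift.** For a true reduction of 0.8 SD, power is 0.82 with no drift, 0.51 with an upward drift of 0.25 SD (net 0.55) and 0.19 with 0.5 SD (net 0.30).

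**4. Can the Off-DBS recording remove the drift?** Suppose a line is fitted to pre-exercise rest windows spanning g minutes and extrapolated G minutes to the post window, with equal independent window noise. With two windows and r = G/g, the variance relative to the raw change is [1 + (1+r)² + r²]/2.

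- g = 30, G = 45: r = 1.5, (1 + 6.25 + 2.25)/2 = 4.75.
- g = 20, G = 60: r = 3, (1 + 16 + 9)/2 = 13.0.

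With ten windows over the same spacings the ratio is 2.5 to 6.6. An effect of 0.78 SD, which the raw test detects with 80% power, then has 12% to 25% power (two windows) or 19% to 43% (ten windows). All spacings are assumed.

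**5. What if power plateaus after DBS-off?** Assume f(t) = 1 − exp(−t/15), no exercise effect, windows at 0, 15 and 30 minutes, and the post window at 75 minutes.

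- Values: f = 0, 0.632, 0.865; f(75) = 0.993.
- Raw change: 0.993 − 0.865 = 0.13 of the total settling.
- Fitted line: mean 0.499 at 15 minutes, slope 0.865/30 = 0.0288 per minute. At 75 minutes it predicts 0.499 + 60 × 0.0288 = 2.23.
- Adjusted step: 0.993 − 2.23 = −1.24 of the total settling.

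Here the adjusted estimate is further from zero than the raw one, and has the opposite sign.

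**The case against.** The strongest reply is that no bias has been shown. The documents give no drift, the percentages rest on assumed sizes, and a single paired test is not the planned two-visit mixed model. The pre window is placed as late as possible in the Off-DBS epoch, which limits any drift that settles early. The randomised FE-versus-VE contrast is sound. All of this stands. It means the figures show sensitivity, not expected bias, but it does not make the primary contrast attributable to exercise.

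Three stronger readings are tempting, and the documents do not support them.

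- **A reader might infer that, because LFPs are streamed throughout, the drift can be estimated and removed.** Pre-exercise data show only the pre-exercise trend. Off-DBS drift during and after exercise is never seen without exercise, and post-exercise data mix drift with any fading of an exercise effect. Extrapolation is imprecise and can overshoot (steps 4 and 5). The length of the Off-DBS epoch and the amount of quiet rest in it are not in the text, the session figure is not shown, and assessments may occupy part of that epoch.
- **A reader might infer that the design favours a false reduction.** Drift could equally be upward and conceal a real one.
- **A reader might infer that the Visit 2 to Visit 3 change in Off-DBS force tracking measures practice.** It measures change between days, after an earlier exercise session. The confounder is practice or fatigue within a session. The Visit 1 familiarisation trials may reduce practice effects, but they do not estimate them.

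**Conclusion.** The concern holds in a limited form. The pre-to-post contrasts in Aims 1 and 2 are fully confounded with at least 40 more minutes since DBS-off and medication withdrawal. That follows from the fixed epoch order and from exercise at every session, and needs no assumption about drift. The consequence does depend on assumptions: at n = 15 with a two-sided 5% paired test, a downward drift of 0.2 to 0.5 SD gives a false reduction in 11% to 44% of trials against 2.5% nominal, while an upward drift costs power. Neither the size nor the direction of drift can be taken from the documents.

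The existing recordings support a partial, descriptive check and not a correction. The FE-versus-VE contrast is protected against drift common to both visits.

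**What to change.** 1. In Aims 1 and 2, state that the pre-to-post result estimates *change over the session*, and reserve causal wording about exercise for the randomised FE-versus-VE contrast.
2. Prespecify that the trend in resting band power across artifact-free rest segments of the pre-exercise Off-DBS epoch, at both visits, is reported beside the primary result. Say that a flat trend supports, but does not prove, the absence of drift. If too little quiet rest is available to estimate a trend, report that.
3. If a linear extrapolation past exercise is presented at all, label it a sensitivity analysis and state its linearity assumption. It should not replace the raw change as the corrected estimate.
4. Do not present the Visit 2 to Visit 3 Off-DBS change as an estimate of within-session practice.

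The cost is a more modest primary conclusion and a little extra analysis of signals already streamed. No further visit or patient is needed. The changes limit what is claimed; they do not remove the confounding, which only a time-matched Off-DBS session without exercise could address directly.

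### Aim 2 names a relationship between STN neural change and motor and clinical change, but no analysis in the posted document relates the two

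*Combined protocol and SAP*

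**What the plan says.** The Aim 2 heading sets the objective: "To determine the relationship between changes in STN neural activity associated with FE and VE on upper extremity motor function" and on the clinical symptoms of PD. The quantity named is change in STN activity, set against function and symptoms.

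The Statistical Analysis paragraph under Aim 2 then plans the following:

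- **Time points:** "Data from the Off DBS and Off DBS + Post Exercise sessions will be used for the primary analysis".
- **Force tracking:** "Mixed effects models will be utilized to determine if force tracking performance improves following either exercise mode compared to Off-DBS", with a secondary comparison of FE against VE.
- **Clinical data:** "Clinical data from the same time points will be evaluated to determine the overall clinical response to high intensity exercise", again with a comparison by exercise mode.
- **Covariates:** "Mixed models will be adjusted for confounding characteristics determined a priori, including sex, education, and PD severity".
- **Checks:** model assumptions and fit, with transformation if needed.

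Under Aim 1, band powers are "calculated at rest for 90 seconds in the Off DBS session immediately prior to exercise and immediately following FE and VE sessions", and "Mixed effect models will be utilized for each band power to determine if band powers at rest while Off DBS are significantly reduced" after exercise, with FE against VE as the secondary question.

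The LFP outcomes text in Data Collection adds comparisons of oscillatory activity across the four epochs, beta-burst dynamics in each condition, and spectrograms: "Triggered spectrograms will be calculated for each trial using the multitaper method".

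**The concern.** Aim 2 is one of two aims, and the only one that ties STN physiology to function. Showing that exercise changes band power and that exercise changes force tracking answers two separate questions. Neither tells us whether patients, or visits, with a larger neural change also show a larger motor change.

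If the plan is followed exactly, the named relationship gets no estimate. If an association is examined anyway, nothing fixes which one. The candidates include five bands plus bursts (6 neural measures), two hemispheres, and three outcomes (TWR, RRMSE and MDS-UPDRS-III, the last standing for the clinical scores). That is already 6 x 2 x 3 = 36 pairings before any choice of model, and a result selected from these would be hard to interpret.

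**Working it through.** **Step 1: what each planned analysis contains.** The documents give no power, alpha or effect size for Aim 2, so there is no figure to reproduce. The check is of the text.

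| Place | Outcome | Explanatory terms | Neural and motor/clinical together? |
|---|---|---|---|
| Aim 2, force tracking | TWR and other force outcomes | pre/post, FE vs VE, confounders | No |
| Aim 2, clinical data | clinical scores | pre/post, FE vs VE | No |
| Aim 1 | each of five band powers | pre/post, FE vs VE | No |
| LFP outcomes | band power, bursts, spectrograms | epoch or condition | No |

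Three places could be mistaken for the missing analysis.

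- The LFP text uses the word relationship, but for oscillatory changes across epochs.
- It mentions a link between beta bursts and bradykinesia, but as earlier data that justify measuring bursts.
- The Aim 2 covariate list is open-ended, but it is a list of confounders. PD severity as a covariate is adjustment, and neural change cannot be presumed to be an unlisted confounder when it is the quantity the aim names.

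**Step 2: are the data there?** Fifteen patients each attend one FE and one VE visit. Resting band power and force tracking are both planned before and after exercise. That gives at most 15 x 2 = 30 pairs of change scores.

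**Step 3: precision of an added model.** Assumptions, not in the documents: two-sided 5%, 80% power, 15 completers, 8:7 order split, normally distributed predictor. The model is change in motor outcome on change in neural measure, with mode, visit and patient, and neural change split into within- and between-patient parts.

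- *Within-patient slope.* Patient, mode and visit terms have rank 17 in 30 rows. Adding the slope gives 18, which leaves 30 - 18 = 12 df. Equivalently, there are 15 FE-minus-VE differences, less intercept, order and slope: 15 - 3 = 12.
- *Between-patient slope, unadjusted.* There are 15 patient means. Mode and visit cancel because every patient has one of each. This leaves 15 - 2 = 13 df.

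Power is the average of P(|T_df(ncp)| > t_crit), where ncp = r/sqrt(1 - r^2) x sqrt(S) and S follows a chi-square distribution with df + 1 degrees of freedom. Solving for 80% power:

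| Slope | df | Detectable partial correlation | Power at r = 0.5 |
|---|---|---|---|
| Within-patient | 12 | 0.671 | 47% |
| Between-patient, unadjusted | 13 | 0.652 | 50% |

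The 95% interval for an observed r = 0.5 is tanh(atanh(0.5) ± 1.96/sqrt(df - 1)). At 12 df this is tanh(0.549 ± 0.591), or -0.04 to 0.81.

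The two rows describe different quantities and should not be merged. The within-patient slope is free of stable patient confounders but uses only the FE-minus-VE difference in change. The between-patient slope reflects each patient's average response to exercise but can be confounded.

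**The case against.** The strongest reply concerns the aim's wording. Its grammar is garbled (a relationship between one thing on another) and may simply mean the effect of exercise on motor function and symptoms. On that reading the planned models deliver what was intended and the fault lies in the sentence stating the aim. This stands as a reason to give rewording equal standing with a new analysis. It does not remove the point, because the aim as printed names changes in STN activity and the analysis beneath it contains none.

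A second reply is that the posted document may be an extract, since it refers to a human-subjects section that is not in it. That limits the statement to the posted document, but it is no evidence that the analysis exists elsewhere. The Aim 2 paragraph itself reads as complete.

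A reader might infer more than the text supports in two ways. One is that the gap undermines the Aim 1 primary outcome or the Aim 2 exercise effects. It does not, because those models are unaffected by the absence of another. The other is that the investigators intend to infer a relationship from two averages moving together. The protocol nowhere says so.

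**Conclusion.** The point holds, and the plan should be changed. In the posted document, no planned analysis relates neural change to motor or clinical change, although Aim 2 names that relationship and the paired data will exist. This is a mismatch between an aim and its analysis. It leaves the aim without an estimate, or open to an association chosen from many after the data are seen. No planned estimate is biased and no primary result is invalidated.

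This conclusion rests on the text alone. The precision figures only indicate what an added model could deliver, under the assumed 5% level, 80% power and 15 completers. Only strong partial correlations, about 0.67 within patients or 0.65 between patients, would be reliably detected. Fewer completers, or further covariates in the between-patient part, would make the figures worse.

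**What to change.** Either of two changes closes the gap.

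**Option 1: add one prespecified association model.** Keep the existing models. For each patient-visit, regress post-minus-pre change in one named force-tracking outcome on post-minus-pre change in one named resting band-power measure.

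- Include exercise mode and visit as fixed effects and a random patient intercept. Split neural change into within- and between-patient parts, and name in advance which slope is the main one.
- State the hemisphere. Use the same bipolar channel before and after exercise and at both visits. The plan selects the highest-beta channel in the Off-DBS epoch, which occurs at each visit, and does not say whether the choice is repeated.
- State the power scale: for example log absolute band power, or the plan's relative power with one normalising period spanning both pre and post. Normalising pre and post separately could remove the change being studied.
- Report the main slope with a 95% CI. Treat other bands, bursts, the other force outcome and MDS-UPDRS-III as exploratory.

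Band, hemisphere and outcome are the sponsor's choice, provided they are fixed before the data are examined. If the data have already been examined, label the model post hoc.

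**Option 2: reword Aim 2.** State it as exercise effects on motor and clinical outcomes, and claim no neural-motor relationship.

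**Cost.** Option 1 needs added analysis text and one model on data already collected, with no new patients or procedures. Its drawback is low precision, so it should be presented as an estimate. Option 2 costs one sentence, but gives up the question that links physiology to function.
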